### **1.2.8 NYU S14-00208/ NCT02221739: Ipilimumab and local RT in chemo-refractory metastatic NSCLC**

NYU S14-00208/NCT02221739 was a single institution prospective trial that tested the hypothesis that the addition of local radiotherapy to a metastatic site in metastatic chemo-resistant NSCLC could enhance the ORR of CTLA-4 blockade by ipilimumab. Patients needed to have progressed after at least one cycle of chemotherapy. Additional eligibility criteria included measurable disease in at least 2 sites, controlled brain metastases and ECOG PS 0-2. The study was a Phase II, optimal two-stage Simon design; 10 patients were to be treated in stage 1 at 6Gy x5; if no grade  $\geq 3$  toxicities, 10 additional patients treated at 9.5Gy x3; ipilimumab 3mg/kg q3 weeks x4 infusions. If  $\geq 1$  abscopal responses in stage 1, the trial was to proceed to enroll an additional 19 patients. Primary endpoint was response per RECIST v1.1 (baseline and post treatment PET/CT) Secondary endpoint was best abscopal response, as well as immunologic biomarkers. Thirty-nine patients accrued to the trial: only 18 were able to complete treatment of radiotherapy plus 4 cycles of Ipilimumab, mostly due to the advanced ECOG score inclusion of that trial (ECOG eligibility up to 2). Based on intent to treat ORR was 18%(7/39). In addition, ORR was 33% among the 18 patients who completed treatment: there were 2 CR, 5 PR, 5 SD and 9 PD. Figure 1 shows the waterfall plot of response for the study, as measured in lesions

outside the irradiated field (abscopal response). Figure 3 demonstrates at a 1-year median follow up a survival difference between the patients who progressed versus the responders. Median survival is still not reached for CR/PR/SD versus 9 months for patients with PD (log-rank test:  $p = 0.016$ ; HR = 9.174).

[figure not shown]

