**Figure 8.**

	Nivo 3 Q2W + Ipi 1 Q12W (n = 38)	Nivo 3 Q2W + Ipi 1 Q6W (n = 39)	Nivo 3 Q2W (n = 52)
Confirmed ORR, % (95% CI)	47 (31, 64)	39 (23, 55)	23 (13, 37)
Median duration of response, mo (95% CI)	NR (11.3, NR)	NR (8.4, NR)	NR (5.7, NR)
Median length of follow-up, mo (range)	12.9 (0.9–18.0)	11.8 (1.1–18.2)	14.3 (0.2–30.1)
Best overall response, %			
Complete response	0	0	8
Partial response	47	39	15
Stable disease	32	18	27
Progressive disease	13	28	38
Unable to determine	8	15	12
Median PFS, mo (95% CI)	8.1 (5.6, 13.6)	3.9 (2.6, 13.2)	3.6 (2.3, 6.6)
1-year OS rate, % (95% CI)	NC	69 (52, 81)	73 (59, 83)

NC = not calculated (when ~25% of patients are censored); NR = not reached  
Combination data based on a February 2016 database lock; monotherapy data based on a March 2016 database lock except for OS data, which are based on an August 2016 database lock

8

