Assessment of response: Response is defined as an objective radiographic response of the measurable metastatic site(s) outside the radiation field evaluated by CT at 3 months after the start of treatment. Lesions will be measured using RECIST 1.1 [52] and best response (PR + CR) based on these criteria will be recorded. To reduce confounding, the irradiated lesion will be excluded from baseline measurement and measurement for the assessment of in-field response will be recorded separately.

**Objective 2.2:** To enhance the ORR to the combination of Ipi/Nivo in NSCLC by preceding it with a combination of Ipi/RT to convert the irradiated tumor into an in situ vaccine.

The trial is designed to enhance ORR to the combination of Ipi/Nivo, by an initial induction of Ipi/RT to one of the metastatic lesions. Since a) approximately 2/3 of chemo-refractory metastatic NSCLC cancers are expected to express  $<1\%$  PDL1; b) Checkmate 012 demonstrated a 19%

objective response rate (ORR) in these patients and c) our recent study of radiation and ipi demonstrated 18% ORR based on intent to treat, the current trial is powered to test in patients with metastatic NSCLC whether the initial addition of local radiotherapy during ipilimumab can increase the ORR to immune checkpoints independently from PD-L1 expression. In order to test this hypothesis a Simon's two-stage design is chosen for this trial, thus 15 patients will be enrolled in the first stage with an upper limit of 4 responses for 1st stage rejection of the combined regimen. If 5 or more objective responses are seen then the trial will proceed to the second stage and an additional 29 patients with PD-L1 negative tumors will be enrolled and treated, for a total target accrual of 44 evaluable patients. A patient is deemed evaluable if they have measurable disease at baseline and had a 9 week imaging evaluation. To ensure 44 evaluable patients, up to 4 additional patients will be enrolled if necessary to replace patients who withdrew or did not have a 9 week evaluation. If there are more than 44 evaluable patients, the decision rule will be made based on the first 44 evaluable patients. Patients who were replaced because they were not evaluable, will not be part of the denominator.

[figure not shown]
**Objective 2.3:** To explore whether early changes in TCR repertoire in peripheral blood are associated with response to treatment

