### 17.2 Sample size justification

As mentioned, a Simon's two-stage optimal design [65] will be used. The null hypothesis is that the true response rate is 31% will be tested against a one-sided alternative. If there are 4 or fewer responses in the first 15 patients, the study will be stopped. Otherwise 29 additional patients will be accrued for a total of 44 patients. The null hypothesis will be rejected if 17 or more responses are observed in 44 patients. This design yields a type I error of 0.10 and power of 90% when the true response rate is 51%. The target sample size is 44 evaluable patients and up to 48 patients (4 extra patients) will be accrued to account for non-evaluable patients or patients who withdraw prior to the 9-week evaluation.

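### Four replacements cannot guarantee 44 evaluable patients, and the plan has no decision rule for fewer; what that costs depends on how patients without a 9-week scan are counted

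*Combined protocol and SAP*

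**What the plan says.** Section 4.0, Objective 2.2, defines an evaluable patient as one with measurable disease at baseline and a 9-week imaging evaluation. It then says "To ensure 44 evaluable patients, up to 4 additional patients will be enrolled if necessary to replace patients who withdrew or did not have a" scan at that time point. Section 17.2 repeats the allowance: "up to 48 patients (4 extra patients) will be accrued to account for non-evaluable patients or patients who withdraw prior to the 9-week evaluation". Neither place gives an expected non-evaluable rate.

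Objective 2.2 covers a surplus (the first 44 evaluable patients decide) and removes replaced patients from the denominator. It does not cover a shortfall, and it does not say how a fifth non-evaluable patient, who cannot be replaced, is handled. The primary analysis in section 17.3 defines success and failure only for 44 evaluable patients.

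The operating characteristics are in section 17.2. The test is set up as follows: "The null hypothesis is that the true response rate is 31% will be tested against a one-sided alternative". The trial ends at stage 1 when 15 patients yield at most four responders, and goes on to recruit 29 more when they yield five or more. The claim for this rule is: "This design yields a type I error of 0.10 and power of 90% when the true response rate is 51"%. The final success count is 18 or more in the synopsis, section 4.0 and section 17.3, but 17 or more in section 17.2.

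**The concern.** A cap of four extra patients is an allowance, and it only becomes a guarantee if the non-evaluable rate is low. If the trial ends with 40 to 43 evaluable patients, the primary verdict is undefined. A result such as 17 of 41 fails against a fixed 18, yet 17 would have been an admissible pre-specified cut-off at that number. With 17 and 18 both already written in the plan, a choice made after the data are seen would have no error control. The stated 90% power also belongs to exactly 44 evaluable patients.

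**Working it through.** **Inputs.** p0 = 0.31, p1 = 0.51, stop at 4 or fewer of 15, total 44 (section 17.2); success at 18 or more (section 17.3); cap 48 (synopsis, section 17.2). One sentence in section 17.3 gives 23 as the first-stage number; 15, used everywhere else, is used here.

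**1. Reproduce the stated design.** For cut-off r and n evaluable patients,

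P(success) = Σ over x = 5 to 15 of P[Bin(15, p) = x] × P[Bin(n − 15, p) ≥ r − x].

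- n = 44, r = 18: type I error 0.0946, power 0.9000. This matches the stated 0.10 and 90%, with no slack in power.
- n = 44, r = 17: type I error 0.150, power 0.925. This does not meet 0.10.

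**2. Chance of reaching 44.** With independent non-evaluability at rate q and the full 48 enrolled, it is P[Bin(48, q) ≤ 4]. At q = 4/48 = 8.3%, the terms for 0 to 4 losses are 0.015 + 0.067 + 0.143 + 0.200 + 0.204 = 0.629.

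| q (assumed) | P(at least 44 of 48) |
|---|---|
| 5% | 0.91 |
| 8% | 0.66 |
| 8.3% (implied by the cap) | 0.63 |
| 12% | 0.30 |
| 15% | 0.13 |

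The documents give no rate under the plan's own definition of evaluable. The nearest figure is the best-response row in Figure 8 (section 1.4), "Unable to determine 8 15 12" (percent; two ipilimumab/nivolumab schedules, then nivolumab alone). It is only a proxy.

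**3. Shortfall when missing scans are unrelated to response.** Apply the step 1 formula with 18 kept:

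| Evaluable n | Type I error | Power |
|---|---|---|
| 44 | 0.095 | 0.900 |
| 43 | 0.079 | 0.883 |
| 42 | 0.065 | 0.862 |
| 41 | 0.052 | 0.836 |
| 40 | 0.041 | 0.803 |

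Averaged over the evaluable number (48 enrolled, at most 44 used), power is 88.6% at q = 8% and 81.1% at q = 15%.

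**4. Shortfall when unscanned patients are non-responders.** The null appears to be an all-patient rate. The second-line 18% is the intent-to-treat 7/39 (section 1.2.8). Figure 8 keeps undetermined patients in its denominator: 47 + 32 + 13 + 8 = 100 and 39 + 18 + 28 + 15 = 100. If the true all-patient rate is p and every unscanned patient is a non-responder, the rate among evaluable patients is p/(1 − q). At q = 15% this is 0.31/0.85 = 0.365 under the null and 0.51/0.85 = 0.600 under the alternative. The same averaged calculation with 18 kept gives:

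| q | Type I error | Power |
|---|---|---|
| 8% | 0.161 | 0.957 |
| 11.5% | 0.179 | 0.966 |
| 15% | 0.189 | 0.972 |

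The problem then becomes a false positive.

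**The case against.** The strongest reply is that the power loss rests on response being independent of evaluability, which the cited table does not support because it counts undetermined patients as non-responders. This stands. A reader might infer that a shortfall simply costs power. Step 4 shows that power can rise while type I error exceeds 0.10, so the direction is not settled by the documents. Step 4 is itself an extreme, since it treats every unscanned patient as a non-responder.

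A reader might also take 8-15% as the protocol's own non-evaluable rate. It is not: best response undetermined is a different thing from having no 9-week scan, and the percentages come from arms of 38 and 39 patients. The 63% figure needs only the plan's own allowance.

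Nor should the earlier radiotherapy plus ipilimumab trial be used. That "only 18 were able to complete treatment of radiotherapy plus 4 cycles of Ipilimumab" describes treatment completion, not scanning, and section 1.2.8 attributes it mostly to admitting ECOG 2, which this trial does not.

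Finally, the effect can be small: at q = 5% the target is reached 91% of the time, and at q = 8% the average power loss in step 3 is 1.4 points (90.0 − 88.6). Nothing in the plan says that a cut-off would be chosen after the data are seen. The point is that the text does not prevent it.

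**Conclusion.** The point holds in limited form and should be addressed. Replacement up to 48 does not ensure 44 evaluable patients: at the rate the cap implies, the trial falls short about 37% of the time (1 − 0.63), and the primary decision is then unspecified. The consequence lies between two cases. Unrelated missingness with 18 kept costs roughly 1 to 9 points of average power for q of 8-15%, with type I error within its limit. Missingness confined to non-responders takes type I error to about 0.16-0.19. All of this assumes independent non-evaluability, enrolment to the cap, the 4/15 first stage and a final count of 18. The documents do not show which non-evaluable rate or which missingness pattern will apply.

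**What to change.** 1. Reconcile the final count in section 17.2 (17) with the synopsis, section 4.0 and section 17.3 (18). Only 18 of 44 meets the stated type I error of 0.10.
2. In Objective 2.2, describe 44 evaluable as a target and say that 90% power applies only at that number.
3. Pre-specify the shortfall rule, tied to the denominator:
   - **Preferred:** count treated patients without a 9-week scan as non-responders. The denominator stays at 44 with 18, and no table is needed.
   - **If the evaluable-only denominator is kept:** with the 4/15 first stage, list cut-offs by attained number, as below.

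| Evaluable n | Cut-off | Type I error | Power |
|---|---|---|---|
| 44 / 43 / 42 | 18 | 0.095 / 0.079 / 0.065 | 0.900 / 0.883 / 0.862 |
| 41 / 40 / 39 | 17 | 0.093 / 0.077 / 0.062 | 0.888 / 0.867 / 0.841 |
| 38 | 16 | 0.090 | 0.872 |

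The table must carry the statement that its error rates assume evaluability is independent of response. If unscanned patients are non-responders, lowering the cut-off makes matters worse: average type I error at 15% non-evaluable is about 0.25, against 0.19 with 18 kept. A sensitivity analysis counting unscanned patients as non-responders should therefore be reported beside it.

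The cost is one short rule or table and, with the table, a stated power of about 0.84-0.90 instead of a flat 90%. No extra patients are needed.

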### **5.1 Inclusion Criteria**

- 1) Ability to understand and the willingness to sign a written informed consent document;
- 2) Histologic diagnosis of NSCLC;
- 3) Patients with an EGFR sensitizing mutation must have received an EGFR tyrosine kinase inhibitor (osimertinib, erlotinib, gefitinib or afatinib) and patients with ALK translocation must have received anti-ALK therapy.

- 4) Patients must have at least two distinct lesions, with one of at least 1 cm or larger in its largest diameter. Patients may have additional non-measurable metastatic lesions (e.g., bone metastases);
- 5) If the patient has received prior systemic therapy, an interval of 2 weeks from last therapy is required;
- 6) Patients must have recovered from the toxic effect(s) of the most recent anti-cancer treatment to NCI CTCAE Grade 1 or less (except alopecia).
- 7) Patients must have adequate organ and marrow function as defined by initial laboratory tests:
  - WBC  $\geq 2000/\mu\text{L}$
  - ANC  $\geq 1.5/\mu\text{L}$
  - Platelets  $\geq 100 \times 10^3/\mu\text{L}$
  - Hemoglobin  $\geq 9 \text{ g/dL}$
  - Creatinine  $\leq 1.5 \times \text{ULN}$
  - AST/ALT  $\leq 2.5 \times \text{ULN}$ , or  $\leq 5 \times \text{ULN}$  if liver metastases are present.
  - Bilirubin  $\leq 1.5 \times \text{ULN}$ , (except patients with Gilbert's Syndrome, who must have a total bilirubin  $\leq 3.0 \text{ mg/dL}$ ;
- 8) Performance status ECOG 0-1 or Karnofsky  $\geq 70\%$ ;
- 9) Men and women, ages  $> 18$  years of age;
- 10) Life expectancy  $> 3$  months;
- 11) Patients may have brain metastases if these are stable for at least 2 weeks (including radiosurgery treated lesions) and patients are not symptomatic or steroid dependent; Baseline MRI will be required." Note these lesions are not considered primary targets for the purposes of this protocol.
- 12) Patients in this study may not use vaccines for the treatment of cancer for up to one month before the first dose of ipilimumab. Concomitant systemic or local anti-cancer medications or treatments are prohibited while receiving study treatments.
- 13) Women of childbearing potential (WOCBP) must be using an adequate method of contraception to avoid pregnancy throughout the study and for up to 5 months after the study.  

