## 17.0 STATISTICAL METHODOLOGY

### 17.1 Overview

The primary endpoint of this study is ORR. A response is defined as a PR or CR as a best response (or that has been confirmed). The trial will be considered to be successful if the ORR, originally achieved in similar patient populations of metastatic NSCLC treated in a protocol of Ipilimumab and local radiotherapy to a metastatic lesion, is increased by 20% or more. It is assumed that the ORR in the first-line is 40% and the ORR in the second-line is 18% and that there will be approximately 60% first-line patients and 40% second-line (and beyond) patients. This yields an historical ORR of 0.31 (= (0.60x0.40) + (0.40x0.18)). The trial design is a single arm, multi-center, Simon optimal two-stage design. Tumor responses will be assessed at baseline, at Day 70 ( $\pm$  7 days), and at specified intervals as stated in section 10.0. Patients will be evaluated for response at day 70 day  $\pm$  7 days. Patients will be enrolled in two stages with 15 patients in the first stage, and potentially an additional 29 patients in the second stage. The decision to enroll patients into the second stage will depend on the number of responses observed in the first stage.

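### The response-rate decision drops and replaces up to four patients without a week-9 scan, although at least part of the null rate counts every treated patient

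*Combined protocol and SAP*

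**What the plan says.** Section 4.0, Objective 2.2, defines the analysis set: "A patient is deemed evaluable if they have measurable disease at baseline and had a 9 week imaging evaluation". Up to four extra patients may be enrolled to replace those who withdrew or had no such evaluation, and "Patients who were replaced because they were not evaluable, will not be part of the denominator". Section 17.2 gives the same purpose for the four extra places: they "will be accrued to account for non-evaluable patients or patients who withdraw prior to the 9-week evaluation". The synopsis repeats the plan of 44 evaluable and up to 48 accrued. Section 17.3 (Primary analysis) applies both the stage 1 and the final rule to evaluable patients.

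No section says that a treated patient who dies, deteriorates or withdraws before the week-9 scan counts as a non-responder. No all-treated response rate is planned as a sensitivity analysis.

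On the null, Section 17.1 states: "It is assumed that the ORR in the first-line is 40% and the ORR in the second-line is 18" percent, with an expected 60/40 mix of first-line and later-line patients. The basis of the second figure is explicit. Objective 2.2 says "our recent study of radiation and ipi demonstrated 18% ORR based on intent to treat", and Section 1.2.8 gives it as 7 of 39. Section 17.1 cites no source or denominator for the 40%.

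**The concern.** In a single-arm trial the whole inference is a comparison with a fixed historical rate, so the observed and historical rates must count patients in the same way. Here one component of the null keeps every accrued patient in the denominator, while the trial's own rate leaves out patients without a week-9 scan. Section 8.5 lists reasons for leaving the study that include intercurrent illness, unacceptable toxicity and a change in the patient's condition. Patients lost for such reasons before day 70 are unlikely to be responders. If they are mostly failures, the same regimen scores higher under this rule than it would have on the basis used for the 18%.

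The criterion is the week-9 scan, not the absence of any scan. As worded, it can also exclude a patient whose progression was documented on an earlier unscheduled scan. It does not exclude patients who only interrupt drug, because the Discontinuation Criteria in Section 6.0 keep their tumor assessments on schedule.

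This is the trial's only formal efficacy decision, and the design has little room below its stated 0.10.

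**Working it through.** **Inputs.** Section 17.2: null 0.31, alternative 0.51, one-sided; stop if 4 or fewer of 15 respond; 44 in total. Final cutoff: 18 or more (synopsis, Sections 4.0 and 17.3). Null components: 0.60 × 0.40 = 0.240 and 0.40 × 0.18 = 0.072, sum 0.312, used as 0.31 (Section 17.1). Replacements: k = 0 to 4 (Objective 2.2).

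**Reproducing the plan.** P(reject) = Σ over x = 5 to 15 of P(X₁ = x; n = 15) × P(X₂ ≥ 18 − x; n = 29).
- p = 0.31: 0.0946
- p = 0.312: 0.0996
- p = 0.51: 0.9000

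The stated 0.10 and 90% are therefore met with a cutoff of 18.

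**Basis of the null.** 7/39 = 17.9%, all accrued patients. For the 40%, the only first-line combination results tabulated in this form are in Figure 8 (Section 1.4): response rates of 47% (n = 38) and 39% (n = 39). The best-response rows are 47 + 32 + 13 + 8 = 100 and 39 + 18 + 28 + 15 = 100, where the last term in each is patients whose response could not be determined. Those patients are in the denominator. If the 40% was drawn from this table, the whole null is an all-treated rate.

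**Effect of replacement.** Assume the k replaced patients are all non-responders and the true rate equals the null. The rate among the 44 evaluable patients is then:
- Case A, whole null all-treated: 0.31 × (44 + k)/44
- Case B, only the 18% all-treated, all losses in second line: 0.31 + 0.18 × k/44
- Case C, only the 18% all-treated, losses spread evenly: 0.31 + 0.072 × k/44

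| k | A: rate, type I error | A from 0.312 | B: rate, type I error | C: rate, type I error |
|---|---|---|---|---|
| 0 | 0.3100, 0.095 | 0.100 | 0.3100, 0.095 | 0.3100, 0.095 |
| 1 | 0.3170, 0.113 | 0.119 | 0.3141, 0.105 | 0.3116, 0.099 |
| 2 | 0.3241, 0.133 | 0.140 | 0.3182, 0.116 | 0.3133, 0.103 |
| 3 | 0.3311, 0.156 | 0.163 | 0.3223, 0.128 | 0.3149, 0.107 |
| 4 | 0.3382, 0.181 | 0.189 | 0.3264, 0.140 | 0.3165, 0.112 |

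A simulation of case A, treating 44 + k patients at 31% and removing k random non-responders (400,000 runs), gave 0.114 for k = 1 and 0.186 for k = 4, close to the closed form.

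**Illustration.** 18/44 = 40.9% is a success as written. If four patients had been replaced, it is 18/48 = 37.5% of those treated.

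**The case against.** The strongest reply is that the effect is wholly conditional. Replacements must occur and must be failures. A patient replaced for lack of baseline measurable disease, or one who simply withdrew, need not be a treatment failure, and the documents give no expected attrition. In the mildest case one replacement leaves the error at 0.099, still below 0.10. All of this stands.

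A reader might infer heavy attrition from the prior trial, where only 18 of 39 completed treatment. The documents do not support that. Section 1.2.8 puts the non-completion down "mostly due to the advanced ECOG score inclusion of that trial", and Section 5.1 here requires "Performance status ECOG 0-1 or Karnofsky" of at least 70%. Not completing drug is also not the same as missing a scan.

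The null is itself a rounded assumption. Moving one of 44 patients from second to first line shifts it by 0.22/44 = 0.005, to 0.315, where type I error is 0.107; that matches three replacements in case C. The exact 95% interval for 7/39 is 7.5% to 33.5%. The small movements in case C are therefore within the uncertainty of the null. But that uncertainty is not a reason to add a bias that, if patients without a scan are mostly failures, favors the regimen.

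Finally, the rule is prespecified, consistent across sections and capped at four, and early deaths do enter progression-free and overall survival. That makes the rule transparent, but it does not put the primary comparison on one basis.

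**Conclusion.** The mismatch is real and should be fixed; confidence in its practical size is medium. The denominator rule and the intent-to-treat basis of the 18% are explicit in the text. The size depends on two things the documents do not settle: how many patients will be replaced and why, and the basis of the 40%. Figure 8 favors the all-treated reading (0.113 with one replaced, 0.181 with four) but does not prove it, because Section 17.1 does not say the 40% came from there.

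A reader might infer that the trial's type I error is 0.18. The documents do not support that: it is the value with all four places used, all by non-responders, and the whole null all-treated. With no replacements, or with losses unrelated to response, it stays at 0.095.

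All figures use the cutoff of 18. Section 17.2 says 17, which alone gives 0.150 with no one replaced; that conflict is separate and must be reconciled on its own.

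**What to change.** In Objective 2.2 and Sections 17.2 and 17.3:
1. Base the stage 1 and final rules on the first 15 and first 44 patients who start protocol treatment with measurable disease at baseline.
2. Count as non-responders those with no CR or PR documented on any on-study assessment that qualifies under the plan's best-response definition. This includes patients who die, progress or withdraw before the week-9 scan. Counting everyone without a week-9 scan as a failure would go too far, because the endpoint is best response (Sections 13.4 and 17.1) and a response may be documented on another scan.
3. Replace only patients who never start treatment or who lack baseline measurable disease.
4. Report the evaluable-only rate as a sensitivity analysis, with the number of missing week-9 scans and the reasons.
5. In Section 17.1, state the source and denominator of the 40%, and whether 51% is an all-treated or an evaluable rate.

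**Cost.** The change is to wording, and the reported response rate may be slightly lower. Type I error stays at 0.095, and power stays at 0.90 if 51% is an all-treated rate. If 51% is an evaluable rate, the all-treated alternative is 0.51 × (44 − k)/44. That is 0.4984 with one of 44 unassessed (power 0.87) and 0.4636 with four (power 0.77). In that case power should be restated.
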